## 2.1.3 Recruitment

Subjects will be recruited from NIH Clinical Center hematopoietic stem cell transplant clinics but could be referred from the outside institutions. Study participants will be primarily recruited from the 04-C-0281 cGvHD natural history study protocol, which currently has more than 260 persons registered and enrolls approximately 3 persons per month, most of them with moderate or severe cGvHD. Referrals will be also accepted from the other NIH protocols or from the extramural community. Every effort will be made to screen potential candidates through the existing 04-C-0281 natural history protocol, which is a non-therapeutic study as part of pre-enrollment evaluations. The patient population enrolled on this study is expected to be representative of the population of persons receiving allogeneic hematopoietic stem cell transplantation at the NIH and nationwide.

## 2.2 REQUIRED TESTING AND COUNSELING FOR FCBP AND PARTNERS OF FCBP

- 2.2.1 During study participation and for 28 days following discontinuation of study drug:
  - Pregnancy tests for females of childbearing potential. A female of childbearing potential (FCBP) is a sexually mature female who: 1) has not undergone a hysterectomy or bilateral oophorectomy; or 2) has not been naturally postmenopausal for at least 24 consecutive months (i.e., has had menses at any time in the preceding 24 consecutive months).
  - Pregnancy tests must occur 10 14 days and again within 24 hours prior to initiation of pomalidomide. FCBP with regular or no menstruation must have a pregnancy test weekly for the first 4 weeks and then every 28 days while on therapy (including breaks in therapy); at discontinuation of pomalidomide and at Day 28 post the last dose of pomalidomide. Females with irregular menstruation must have a pregnancy test weekly for the first 4 weeks and then every 14 days while on therapy (including breaks in therapy), at discontinuation of pomalidomide and at Day 14 and Day 28 post the last dose of pomalidomide (see Appendix M: Pomalidomide Risks of Fetal Exposure, Pregnancy Testing Guidelines and Acceptable Birth Control Methods).
  - All patients must be counseled about pregnancy precautions, risks of fetal exposure and other risks. The counseling must be done every 28 days and at drug discontinuation through the POMALYST REMSTM program. See Appendix M: Pomalidomide Risks of Fetal Exposure, Pregnancy Testing Guidelines and Acceptable Birth Control Methods.

#### 2.3 SCREENING EVALUATION

Screening procedures may be performed on a CCR screening protocol, most commonly on 04-C-0281 "Natural History of Chronic GVHD." All studies must be completed within 8 weeks prior to enrollment:

- History and physical exam, Karnofsky performance score
- Documentation of cGvHD diagnosis, NIH organ and global severity stage
- CBC, platelets, differential, PT/PTT, serum chemistries (including sodium, potassium, chloride, CO2, calcium, magnesium, phosphorus, blood urea nitrogen [BUN], creatinine, glucose, albumin, total protein, alkaline phosphatase, total bilirubin, AST [SGOT], ALT

[SGPT], lactate dehydrogenase [LDH], and uric acid), urinalysis, urine pregnancy testing, TSH

- Infectious serology markers (HIV-1, HBV, HCV)
- Determination of estimated creatinine clearance
- Pulmonary function testing, CT of the chest (BOS sequence), cardiac ECHO, ECG
- Social work screening consult

For baseline evaluations, please see Section 2.6.

## 2.4 **REGISTRATION PROCEDURES**

Authorized staff must register an eligible candidate with NCI Central Registration Office (CRO) within 24 hours of signing consent. A registration Eligibility Checklist from the web site (http://home.ccr.cancer.gov/intra/eligibility/welcome.htm) must be completed and sent via encrypted email to: NCI Central Registration Office (HOIS) <[contact]. After confirmation of eligibility at Central Registration Office, CRO staff will call pharmacy to advise them of the acceptance of the patient on the protocol prior to the release of any investigational agents. Verification of Registration will be forwarded electronically via email to the research team. A recorder is available during non-working hours.

#### 2.5 TREATMENT ASSIGNMENT AND RANDOMIZATION PROCEDURES

#### Cohorts

Number	Name	Description
1	cGvHD Patients	Patients with moderate or severe cGvHD as per NIH criteria that has not responded to high-dose corticosteroids or second-line therapy.

#### Arms

Number	Name	Description
1	Experimental 1	0.5 mg/day without Dose Escalation
2	Experimental 2	0.5 mg/day with Dose Escalation by 0.5 mg/day increments every 2 weeks to a maximum of 2.0 mg/day

#### **Randomization and Arm Assignment**

Randomization will be done at the time of enrollment by the Central Registration Office, which will perform the randomization using randomization assignments determined by the study statistician. Subjects will be randomized to one of two treatment arms: low dose (0.5 mg/d) and high dose (0.5, escalating every two weeks to 1.0. 1.5 or 2.0 mg/d) pomalidomide. If one of the arms closes due to futility, toxicity or completion, enrollment will continue to the remaining arm.

#### 2.6 **BASELINE EVALUATION**

Following studies will be performed at the baseline before/after the enrollment and within four weeks prior to starting taking the study drug unless otherwise indicated below:

- History and physical exam, Karnofsky performance score
- CBC, platelets, differential, PT/PTT, serum chemistries (including sodium, potassium, chloride, CO2, calcium, magnesium, phosphorus, blood urea nitrogen [BUN], creatinine, glucose, albumin, total protein, alkaline phosphatase, total bilirubin, AST [SGOT], ALT [SGPT], lactate dehydrogenase [LDH], and uric acid), CRP, total complement and C3 and C4, urine pregnancy testing (once within 10-14 days prior to the start of study drug and again within 24 hours prior to the start of study drug), immunoglobulin levels, TBNK, blood CMV PCR, drug levels if pertinent (e.g., cyclosporine, tacrolimus, sirolimus)
- MRI of the involved extremity if clinically indicated (acceptable if done within 8 weeks)
- Documentation of cGvHD per NIH criteria (diagnostic, distinct, other and common manifestations), NIH organ and global stage, baseline assessments (form A and form B) per NIH response criteria, date of cGvHD diagnosis, prior and current treatments, prednisone or other steroids oral dose, and other patient, donor and transplant characteristics per Appendix Q.
- Specialty evaluations of cGvHD: dermatology, ophthalmology, dental, rehabilitation and occupational therapy, gynecology if applicable (can be done up to two weeks after starting study drug, except for dermatology and dental evaluations which must be done prior to starting study drug)
- Diagnostic and research biopsies of the skin and mouth (all persons), and other organs (only if clinically indicated)
- ECG
- Research laboratory (blood, saliva, urine)
- Study drug dispensation
- Subject diary review
- Documentation of concurrent medications

## **3 STUDY IMPLEMENTATION**

#### 3.1 STUDY DESIGN

The study is a randomized phase 2 trial with the single stage selection design. It is known from prior trials that the maximum tolerated dose of pomalidomide is about 3 mg/d in persons with bone marrow disorders receiving prior therapies for cancer, in cGvHD doses <3mg/d have been well tolerated. This study will explore clinical toxicity of gradual escalation of pomalidomide doses <3 mg/d in subjects with cGvHD. Patients will receive either a constant low dose of pomalidomide (0.5 mg/day) for six months or a strategy of increasing dose of pomalidomide from 0.5 mg/d up through each individual patients' maximum tolerated dose, with escalations by 0.5 mg/d every 2 weeks to a maximum of 2.0 mg/d. In each of the two arms, the trial will use a single stage design.

As an early stopping rule for futility as outlined in section **8**, if after 7 patients have enrolled on either arm, 0 have responded, then no further patients will be accrued to that arm as soon as this can be determined. To protect patient safety, an early stopping rule will be implemented. With two arms, each of which has a maximal accrual of 16 patients, up to 32 evaluable patients will be randomized. Safety assessments and pregnancy testing for FCBP will be performed at scheduled intervals as described in the Study Calendar.

Response will be assessed every 3 months while taking pomalidomide following the criteria in Section 6.2. The primary efficacy endpoint will be evaluated at 6 months. Efficacy outcome is defined as clinical response (CR or PR) in subjects who enter the study with stable cGvHD or stable disease for  $\geq$ 3 mo for subjects with progressive cGvHD at study-entry. (Stability will be assessed by the clinician and by the clinical exam at the screening evaluation based on the clinician estimate of the disease trajectory during the 3 months pre-randomization). Subjects who meet the response criteria at 6 months will continue therapy for another 6 months. If in the subject's best interest, efforts will be made to provide access to study drug on compassionate basis beyond the 12-month study endpoint.

Patients who discontinue therapy for any reason will be followed for up to 24 months after starting pomalidomide as described in Section **6.1.3**.

Concurrent topical and ancillary treatments for cGvHD are allowed per standards of care and will be recorded (see Section 4). Other systemic immune suppression must stay stable or be tapered (systemic immunosuppression taper should be attempted no earlier than after 4-6 weeks on study), throughout the treatment with pomalidomide (with up to 2 steroid pulses allowed for disease stabilization per Section 4.1).

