# **10 STATISTICAL CONSIDERATIONS**

It is known from prior trials that the pomalidomide MTD is about 3 mg/d in persons with bone marrow disorders receiving therapies for cancer. Due to high frequency of pomalidomide dose de-escalation observed in preliminary cGvHD experiences when given at 3 mg/d, this study will explore clinical toxicity of gradual escalation doses below 3.0 mg.

The primary objective of this study is to determine if patients with cGVHD will experience an acceptable level of clinical response when treated with either a constant low dose of pomalidomide (0.5 mg/day) for six months or a strategy of increasing dose of pomalidomide from 0.5 mg/d up through each individual patients' maximum tolerated dose, with escalations by

0.5 mg/d every 2 weeks to a maximum of 2.0 mg/d. The study will thus randomize patients between fixed low dose and escalating dose to tolerance, and will be considered a randomized phase II trial with a selection design component.

In each of the two arms, the trial will be conducted using a single stage design. With 16 patients on each arm, an exact binomial test would have 90% power to detect a difference between a 5% response rate and a 30% response rate using a 0.10 one-sided significance level and an exact binomial test. In addition, after the trial has ended, the 80% and 95% confidence limits will be determined for each arm about the observed response proportion in order to aid in interpretation of the results. If there are 3 or more responses in 16 patients, this would be sufficient to rule out a 5% response rate and demonstrate consistency with 30% or better response rates.

At the conclusion of the study, if both arms are able to accrue to the full 16 patients, the arm with the greater number of responses will be selected for further investigation subsequently. That is, if the fixed, low-dose arm, or the increasing dose level arm, has the greater number of responses, then that arm would be studied further. In the event of a tie, the lower dose arm would likely be preferred. As an example, if the true probabilities of response on the two arms were 0.10 and 0.30, then the probability of correctly selecting the superior arm would be 93%, and if the true probabilities on the two arms were 0.15 and 0.30, the probability of correct selection would be 84%.

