As an early stopping rule for futility, if after 7 patients have enrolled on either arm, 0 have responded, then no further patients will be accrued to that arm as soon as this can be determined. In practice, this means that patients may continue to be accrued beyond 7 in an arm, but no more patients would be registered and treated on that arm once the first 7 were evaluated and no PRs or CRs were identified in those first 7.

To protect patient safety, an early stopping rule will be implemented as follows. For patients treated on either arm, if 2 patients in the first 6, or 33% of the patients at any time experience a DLT at a given dose level, no further patients will be treated at that given level on the trial. Furthermore, when more than 6 patients have received a given dose level, if at any time 33% or more patients experience a DLT when treated at that dose level, then no further patients will be treated at that dose level. Thus, as an example, should there be 2 patients with a DLT in the first 6 who are able to receive 2.0 mg/day on the dose escalating arm, then subsequent patients treated on that arm will not be escalated beyond 1.5 mg/day.

With two arms, each of which has a maximal accrual of 16 patients, up to 32 evaluable patients will be randomized. In order to allow for a very small number of patients who are not able to be evaluated at all for response, the accrual ceiling will be set at 35.

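### One 5% null covers an endpoint that counts stable disease as success for patients progressing at entry, so 3 of 16 rejects a pooled 5% but need not show drug activity

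*Combined protocol and SAP*

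**What the plan says.** Section 3.1 defines the 6-month efficacy outcome with two bars: "Efficacy outcome is defined as clinical response (CR or PR) in subjects who enter the study with stable cGvHD or stable disease". The sentence continues by requiring the stable disease to last at least 3 months and by tying it to patients whose cGvHD was progressive at entry. Section 6.2.2.1 agrees that stable disease counts as a response after documented progression in the preceding 3 months. Sections 2.1.1 and 2.1.2 admit both kinds of patient and set no limit on the mix.

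Section 10 gives one design for everyone. Per arm, "an exact binomial test would have 90% power to detect a difference between a 5% response rate and a 30% response rate"; the test is one-sided at level 0.10. The decision rule is: "If there are 3 or more responses in 16 patients, this would be sufficient to rule out a 5% response rate". Between arms, "the arm with the greater number of responses will be selected for further investigation subsequently". Neither a rate by entry trajectory nor an expected share of progressive entrants is stated. The futility rule in Section 10 counts only PRs and CRs among the first 7 patients.

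Section 2.5 says the Central Registration Office randomizes, "which will perform the randomization using randomization assignments determined by the study statistician". No stratification factor is named.

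**The concern.** A 5% null is meant to be the success rate if the drug does nothing. That is a reasonable kind of figure for CR or PR in refractory disease. For a patient progressing at entry, however, success means that the disease stops getting worse, and several features of the protocol could bring that about without pomalidomide:

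- Other systemic immunosuppression may continue, and Sections 3.1 and 4.1 allow up to two steroid pulses. Section 3.1 gives disease stabilization as their purpose.
- The Appendix I progression thresholds are wide. A skin increase below 25 points of body surface area, or a mouth increase below 3 points, is not progression.
- No passage reports how often progressing cGvHD stabilizes without the study drug.

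If that rate is well above 5%, an arm can reach 3 of 16 with no drug effect, and the main efficacy conclusion for that arm fails. A second, smaller matter is the choice between arms on raw counts: an arm that happens to receive more progressive entrants has an advantage unrelated to dose.

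**Working it through.** **Inputs from Section 10.** n = 16 per arm, null 5%, target 30%, one-sided 0.10, cut-off 3 responses.

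**Step 1: the plan's own figures.** With X ~ Binomial(16, p), P(X ≥ 3) = 1 − P(0) − P(1) − P(2).

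- p = 0.05: 1 − 0.4401 − 0.3706 − 0.1463 = 0.043, below 0.10. A cut-off of 2 would give 0.189, so 3 is the right integer.
- p = 0.30: 1 − 0.0033 − 0.0228 − 0.0732 = 0.901, the stated 90%.
- Selection, comparing two Binomial(16) counts with ties split equally: 0.925 for 0.10 against 0.30, and 0.845 for 0.15 against 0.30. The plan states 93% and 84%.

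The stated figures reproduce.

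**Step 2: the same rule applied to a mix.** Let k of 16 patients be progressive at entry, with no-drug success probability q, and let the other 16 − k have 5%. Then X = Binomial(16 − k, 0.05) + Binomial(k, q). The documents give neither k nor q, so both are assumptions shown over a range.

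Example, k = 8 and q = 0.20. The stable half gives 0, 1 or 2 successes with probability 0.6634, 0.2793, 0.0515. The progressive half gives 0.1678, 0.3355, 0.2936.

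- P(0) = 0.6634 × 0.1678 = 0.1113
- P(1) = 0.6634 × 0.3355 + 0.2793 × 0.1678 = 0.2694
- P(2) = 0.6634 × 0.2936 + 0.2793 × 0.3355 + 0.0515 × 0.1678 = 0.2971
- P(X ≥ 3) = 1 − 0.6778 = 0.322

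P(at least 3 of 16) with an inactive drug:

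| q (assumed) | k = 4 | k = 8 |
|---|---|---|
| 5% | 0.043 | 0.043 |
| 10% | 0.073 | 0.113 |
| 20% | 0.154 | 0.322 |
| 30% | 0.259 | 0.560 |
| 40% | 0.381 | 0.760 |

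**Step 3: cut-off needed to keep 0.10.** Power is for a gain of 25 points in both strata.

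| q (assumed) | k = 4: cut-off, alpha, power | k = 8: cut-off, alpha, power |
|---|---|---|
| 10% | 3, 0.073, 0.918 | 4, 0.027, 0.816 |
| 20% | 4, 0.040, 0.845 | 5, 0.036, 0.781 |
| 30% | 4, 0.083, 0.894 | 6, 0.036, 0.749 |
| 40% | 5, 0.038, 0.821 | 7, 0.031, 0.721 |

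**Step 4: chance imbalance between arms.** If K of 32 patients are progressive and 16 go to each arm, the number in one arm is Hypergeometric(32, K, 16). The arms differ by 4 or more with probability 0.220 (K = 8) to 0.289 (K = 16).

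The table gives correct selection (ties halved, K = 16), first at an 8:8 split and then averaged over unstratified allocation. Response rates are assumed, inferior arm against superior arm.

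| Stable entrants | Progressive entrants | 8:8 split | Unstratified average | Loss (points) |
|---|---|---|---|---|
| 0.10 / 0.30 | 0.30 / 0.50 | 0.899 | 0.893 | 0.6 |
| 0.10 / 0.30 | 0.40 / 0.60 | 0.896 | 0.883 | 1.3 |
| 0.15 / 0.30 | 0.40 / 0.55 | 0.821 | 0.812 | 0.9 |
| 0.15 / 0.30 | 0.30 / 0.45 | 0.826 | 0.822 | 0.4 |

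**The case against.** A reader might infer that 3 of 16 does not rule out a 5% response rate once some responses are stable disease. The documents do not support that. Step 1 gives 0.043 at a pooled 5%. If the pooled rate is 5% but unequal by stratum, the test is conservative: 8 patients at 10% and 8 at 0% give 0.038. The statement in Section 10 is correct for the rate it names. What is unsupported is the benchmark.

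A reader might also infer that unstratified randomization is likely to pick the wrong arm. With two identical inactive arms split 10 to 6 on progressive entrants (q = 30%, stable 5%), the arm with 10 has more responses 60% of the time against 23%. But neither choice is wrong when the arms are identical, and the figure is conditional on the imbalance. Averaged over allocations, the loss in Step 4 is 0.4 to 1.3 points. The statistician's list may also be stratified without the protocol saying so.

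Other points on the plan's side stand in part:

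- The progressive bar is not trivial. It needs at least 3 months of stability, mixed responses count as progression, prior treatment must have failed, and no systemic therapy may have started in the preceding 4 weeks. These lower q by an unknown amount.
- At k = 4 and q = 10% the error rate is 0.073, within plan.
- The planned 95% limits at 3 of 16 run from 4.0% to 45.6%, so the weakness of the evidence would be visible. The limits would still not separate stabilization from CR/PR.

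**Conclusion.** The point holds as a gap in justification, not as a calculation error. The rule is correctly computed for a pooled 5%, but 5% is not supported as the no-drug rate for an endpoint that includes stabilization, so meeting the cut-off need not show activity.

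The size rests on two quantities the documents do not give. With 5% in stable entrants and 10% to 40% no-drug stabilization in progressive entrants, the false-positive rate is 7% to 38% at 4 of 16 progressive and 11% to 76% at 8 of 16, against a ceiling of 10%. Given 5% in stable entrants, it stays at 4.3% only if progressive entrants also have a 5% null. This problem needs no imbalance and applies to each arm separately.

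The futility count of PRs and CRs in Section 10 also does not match the endpoint in Sections 3.1 and 6.2.2.1, which suggests that the two-bar definition was not carried through to the statistical section. Lack of stated stratification is a minor companion issue.

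**What to change.** In Section 10:

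1. Report responses per arm by entry trajectory, with CR/PR successes separate from stable-disease successes. Overall response category (Section 6.2.2) and entry trajectory (Section 3.5) are already collected, so this can be done even if accrual is complete.
2. Either confine the conclusion about excluding 5% to CR/PR successes, or state and justify a null for stable disease in progressive entrants and recompute the cut-off and power as in Step 3.
3. Reconcile the endpoint in Sections 3.1 and 6.2.2.1 with the PR-and-CR futility count.

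As a secondary step, if randomization is still open, stratify the list in Section 2.5 by trajectory, with the label fixed before assignment. Section 3.1 places that judgement at screening, while the calendar in Section 3.5 ticks trajectory at baseline and randomization at screening. These must be reconciled first. Stratifying guards against a bad split but gains only about 1 point of correct selection on average, and it does not repair the null.

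The cost is one table, some text and, for the secondary step, two lists instead of one. No patients or procedures are added. The real downside is a less favourable conclusion. Power falls to between 0.72 and 0.92 under Step 3. If only CR/PR counts and part of the 30% target was stabilization, power also drops. For an assumed CR/PR rate of 25% it is 1 − 0.0100 − 0.0535 − 0.1336 = 0.80, and for 20% it is 1 − 0.0281 − 0.1126 − 0.2111 = 0.65.

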## **Study Schema**

#### 3.1.1 Dose-Limiting Toxicity

DLT will be defined as any grade  $\geq 3$  adverse event which is thought to be probably or definitively related to the investigational drug administration (notable exceptions where grades 2 or lower can be considered as DLTs are indicated in Table 4 below in Section 3.3). In addition, any persons who are unable to tolerate the dose to which they are assigned will be counted as a DLT at the maximum dose explored for that patient. The time frame for evaluation in which toxicity will count towards a DLT will be up to 28 days after therapy received at a given dose

level. In addition, a grade  $\geq$  3 AE will not be considered as DLT if the adverse event is attributed to a GVHD flare and responds to steroid pulse therapy as outlined in section 4.1. Whether treated on either arm, if there are 2 patients in the first 6 who experience a DLT from a given dose level, then no further patients will be treated at that dose level on the trial, regardless of arm. Furthermore, when more than 6 patients have received a given dose level, if at any time 33% or more patients experience a DLT when treated at that dose level, then no further patients will be treated at that dose level, then no further patients will be treated at that dose level, then no further patients will be treated at that dose level, then no further patients will be treated at that dose level, then no further patients will be treated at that dose level, then no further patients will be treated at that dose level. Data from all subjects who receive  $\geq$ 1 dose of pomalidomide will be include in the safety analysis.

